## 1. VERSION HISTORY

This Statistical Analysis Plan (SAP) for study B9991004 is based on the protocol amendment 8 dated 27-Feb-2019.

**Table 1. Summary of Major Changes in SAP Amendments**

Version	Version Date	Summary of Changes
6	22-Feb-2022	
Section 2 “Introduction” - this section was modified to indicate that the primary analysis will occur after last subject last visit across all tumor types and combinations.
 
Section 6.4 “Subset Analyses” - relapse and resistant categories for prior checkpoint inhibitor status are now combined.
 
Section 6.2.6.1 “Time to and Duration of ADA” - removed text regarding assessments after discontinuation for censoring.
 
Section 6.2.2.6 “Overall Survival” - added the following text “OS analysis will be conducted for patients up to LSLV of the study”.
 
Minor editorial and consistency changes throughout the document.

5	17-Dec-2020	
Section 3.4.2 “Baseline characteristics” - removed “physical measurements”.
 
Section 6.2.2.3 “Duration of response” - removed listing for DR.
 
Section 6.2.2.5 “Progression-free survival” - removed time of follow-up for PFS.
 
Section 6.2.2.6 “Overall survival” - removed time of follow-up for OS.
 
Section 6.2.3 “Pharmacokinetic endpoints” - removed linear-linear and log-linear PK plots.
 
Section 6.2.6.3 “Analysis of PK by immunogenicity status” - removed data listing for immunogenicity and relevant PK and safety data; removed “safety” from header.
 
Section 6.2.6.3 “Analysis of PK by immunogenicity status” - removed safety and immunogenicity summaries; removed log-linear plots.
 
Section 6.4 “Subset Analyses” - combined subset of prior PD-1 and PD-L1 into PD-1/PD-L1; added in PD-L1 subset analysis and CD8 descriptive analysis by OR.
 
Section 6.5.1 “Baseline summaries” - updated listing to Prior anti-cancer drug therapies.
 
Section 6.5.1.1 “Demographic characteristics” - removed reference to “physical measurements”, and to height, weight, BMI and BSA.
 
Section 6.5.4 “Concomitant medications and non-drug treatments” - removed prior medication summaries and listings; removed anti- cancer treatment listings.
 
Section 6.6.1.1 “All adverse events” - removed summary of TEAE leading to interruption of individual study drugs and included any study drug; Removed redundant summary for TEAE; removed summaries for TEAEs by SOC and PT related to each study drug; added TEAEs related to any study drug by SOC and PT and grade.
 
Section 6.6.1.2 “Adverse events leading to interruption of study treatment” - removed summary of TEAE leading to interruption of CMP.
 
Section 6.6.5.1 “Hematology and chemistry parameters” - removed summary of laboratory parameters by CTCAE grade table.
 
Section 6.6.4 “Other significant adverse events” - removed summary of irAE (and IRR) leading to discontinuation of a study drugs (except Avelumab); removed summary of irAE (and IRR) by death and grade <math>\geq 3</math>.
 
Section 6.6.5.2 “Other laboratory parameters” - removed listing of abnormal values for hematology, chemistry, urinalysis, and coagulation.
 
Section 6.6.6 “Vital signs” - removed vital signs summaries.

		
Section 6.6.7 “Electrocardiogram” - removed ECG listings and ECG summaries by timepoint.
 
Table 15 “Case Definition for irAEs” - added in “Steps 3 and 4 will be checked concurrently. Step 5 will be checked if the criteria in Step 4 is met, irrespective of whether the Criteria in Step 3 is met”.

4	10-Jun-2019	
Updated study objectives (Section 2.1), endpoints (Section 3.1, Section 3.3, Section 6.3), study design (Section 2.2), study treatments (Section 3.4.1), definition of DLT-evaluable set (Section 4.3.1), sample size (Section 5.1.1), decision rules (Section 5.1.2) and associated statistical considerations (Section 6 and subsections) as per revisions in Protocol Amendments 6 through 8.
 
In addition, the following updates were made to the SAP.
 
Sections 3.2.2 and 6.2.3 “Pharmacokinetic endpoints” – aligned content of Table 2 and associated analyses to the protocol-specified endpoints.
 
Section 3.2.3 “Immunogenicity endpoints”, Section 4.3.4 “Immunogenicity analysis set”, Section 6.2.6 “Endpoints for immunogenicity data of avelumab and other study drugs” – deleted reference to neutralizing antibodies (nAb) since not specified in the protocol.
 
Section 3.4.1 “Study drug, study treatment and baseline definitions” – added definition of baseline for immunogenicity analyses.
 
Section 3.5 “Adverse Events” - the definition of Treatment-emergent adverse events (TEAEs) was modified to include all AEs with onset date during the on-treatment period. Cytokine Release Syndrome was added as an AE of special interest for Combination F.
 
Section 5.2.10 “Adequate baseline tumor assessment” - the criteria were updated to include only criteria that can be derived programmatically.
 
Section 5.3.3.1 “Date of last contact” – added withdrawal of consent date in the derivation of date of last contact.
 
Section 5.3.3.4 “Date of start of new anti-cancer therapy” – revised to include additional details of imputation rules for incomplete dates for start date of new anti-cancer therapy.
 
Section 6.2.2.3 “Duration of response” – added details regarding censoring for duration of response since “no adequate baseline assessment” which is used in censoring for PFS analyses is not applicable to analyses of duration of response for patients with objective response. Updated the time points for derivation of DR rates to be aligned with the schedule of tumor assessments.
 
Section 6.2.2.5 “Progression-free survival” - updated the time points for derivation of PFS rates to be aligned with the schedule of tumor assessments; added further details for summary of time of follow-up for PFS.
 
Section 6.2.2.6 “Overall survival” – updated the time points for derivation of OS rates; added further details for summary of time of follow-up for OS.
 
Section 6.2.5 “Biomarker endpoints” – simplified analyses to include only descriptive summaries.
 
Section 6.2.6 “Endpoints for immunogenicity data of avelumab and other study drugs”- added details for the analyses of ADA.
 
Section 6.5.1.3 “Disease characteristics” – simplified summaries for smoking history.
 
Section 6.5.1.4 “Prior anti-cancer therapies” – aligned with data collected in eCRF.
 
Section 6.5.2.1 “Patient disposition” – deleted references to randomization stratification factors since not applicable to the study.
 
Section 6.5.3 “Study treatment compliance and exposure” – added derivations for CMP-001 as per Protocol Amendment 8; deleted by-cycle summaries; deleted summaries for dose omissions, dose delays, infusion rate reductions and


		
infusion interruptions since such changes are captured in the overall derivation of relative dose intensity.
 
Section 6.6.1 “Adverse events” and subsections – updated definition of treatment-emergent adverse event; added summaries of AEs leading to interruption of study drug; added summaries for cytokine release syndrome (Combination F only); given the nature of immune-related AEs (irAEs) and infusion related reactions (IRRs), removed the summaries of treatment-related irAEs and treatment-related IRRs; removed the requirement that all summaries by SOC and PT will be replicated by PT only.
 
Section 6.6.2 “Death” – deleted references to primary reason for death since not collected in the eCRF.
 
Section 6.6.5 “Laboratory data” and subsections –added summary for patients with newly occurring or worsening laboratory abnormalities; updated lab parameters as per protocol; deleted summaries of laboratory data by time point since the data can adequately be characterized and interpreted based on CTCAE grade and shift tables to low, normal and high for parameters that are not graded per CTCAE.
 
Section 6.6.7 “Electrocardiogram” – deleted QTcP since the number of patients enrolled in each cohort is small.
 
Section for “Physical Examination” was removed as data not collected in the eCRF (abnormal findings are reported as AEs).
 
Section 8 ”References” – references updated.
 
Appendix 1 “Immune-related Adverse Events” – updated the ATC codes for concomitant medications in Step 4 of the case definition for irAEs and added a statement regarding medical review if needed to refine the programmatic derivation.
 
Minor editorial and consistency changes throughout the document.

3	06-Dec-2016	
Updated objectives, endpoints, study design, sample size and other statistical considerations as per revisions in Protocol Amendment 5, namely as it pertains to the addition of the SCLC and 1L NSCLC cohorts in Phase 2 of Combination A, addition of Combinations C and D. Additional changes and updates described below.
 
Section 2 “Introduction” – changed the cut-off date for the primary CSR from 12 to 18 months after last patient first treatment to allow for efficacy data to mature and to have longer follow-up for safety.
 
Section 3.4.1 “Study drug, study treatment and baseline definitions” – added definition of end date of study treatment; referred to RR instead of heart rate in ECG baseline derivations since the CRF collects RR rather than heart rate.
 
Start of new anti-cancer drug therapy and start of new anti-cancer therapy are added in Sections 5.2.5 and 5.2.6, respectively.
 
Section 5.2.10 “Adequate baseline tumor assessment” and 5.2.11 “Adequate post-baseline tumor assessment” were added
 
Section 5.3.3.4 “Date of start of new anti-cancer therapy” was added to provide details of imputation rules for incomplete dates for start date of new anti-cancer therapy (drug therapy, radiation, surgery).
 
Section 6.1.2.1 “Primary analysis” of OR by investigator assessment – added an additional reason for BOR of NE associated with inadequate or missing baseline assessment; included an additional reason for NE associated with death prior to first post-baseline tumor assessment; added definition of BOR of non-CR/non-PD for patients without measurable disease at baseline.
 
Section 6.2.2.2 “Disease control” –corrected the definition of DC to include BOR of non-CR/non-PD to take into account patients without measurable disease at baseline.

		
Section 6.2.2.5 “Progression-free survival” – provided more details and hierarchy associated with the derivation of reasons for censoring.
 
Section 6.2.2.6 “Overall survival” – provided more details and hierarchy associated with the derivation of reasons for censoring.
 
Section 6.3.1 “irRECIST endpoints” – added irNE as a category for irBOR and provided more details for outcome and event dates for irPFS and irDR as was done for PFS and DR.
 
Section 6.4 “Subset Analyses” – added subcategories to prior checkpoint inhibitor status (now includes relapsed, refractory, resistant, naïve).
 
Section 6.5.1.1 “Demographic characteristics” – added Middle East as another possible geographic region and changed the geographic region Australia to Australasia.
 
Section 6.5.1.3 “Disease characteristics” – added time since diagnosis of local/regional recurrence of disease.
 
Section 6.5.1.4 “Prior anti-cancer therapies” – clarified that prior anti-cancer therapies will be listed together with concomitant and follow-up therapies but with a flag to identify them as prior therapies. Removed the summary of prior anti-cancer drug therapies and radiotherapy due to the first-line setting of the study.
 
Section 6.5.2.1 “Patient disposition” –clarified the summary descriptions to match the CRF data collection and descriptors
 
Section 6.5.3 “Study treatment compliance and exposure” – provided details regarding cycle derivations
 
Section 6.5.3.6 “Dose omissions” and Section 6.5.3.9 “Infusion interruptions” were added.
 
Section 6.5.3.7 “Dose delays” – provided further derivation details.
 
Section 6.5.3.8 “Infusion rate reductions” – added further derivation details.
 
Section 6.5.4 “Concomitant medications and non-drug therapies” – non-drug treatments will be listed but not summarized
 
Section 6.5.5 “Subsequent anti-cancer therapies” – deleted the summary of BOR across all anti-cancer drug therapies since not meaningful from a clinical standpoint.
 
Section 6.6.1 “Adverse events” and subsections – corrected details associated with irAE and IRR based on FDA feedback.
 
Section 6.6.5 “Laboratory data” and subsections –corrected the descriptor of the eDISH plot; changed the formula for corrected calcium to be expressed in SI units; clarified that the denominator to calculate percentages for each laboratory parameter is the number of patients evaluable for the particular summary.
 
Section 6.6.7 “Electrocardiogram” – clarified that the denominator to calculate percentages for each category is the number of patients evaluable for the particular summary. Deleted the summary for patients with ECG abnormalities based on morphology since collected in a free text field.
 
Section 9 “Appendices” – added appendices with the irAE and IRR derivation rules; deleted the tabulation of cycle derivations since included with more details in the exposure section.
 
Minor editorial and consistency changes throughout the document.

2	01-Apr-2016	
Changed objectives, endpoints, and other statistical considerations as per revisions in Protocol Amendment 2
 
Phase 2 study design for Combination A updated to include TNBC cohort.
 
Phase 1b dose-escalation lead-in and Phase 2 for Combination B added to study design.
 
Analysis sets updated to include those for Combination B.

		Added statistical methods and decision rules for Combination B. Updated to include sample size determination for the TNBC cohort for Combination A and sample size determination for Combination B. Updated to include Combination B in efficacy analysis. Updated document throughout to include specific details for Combination B.
1	03-Sep-2015	Original SAP

## 2. INTRODUCTION

This SAP provides the detailed methodology for summary and statistical analyses of the data collected in study B9991004. This document may modify the plans outlined in the protocol; however, any major modifications of the primary endpoint definition or its analysis will also be reflected in a protocol amendment.

Statistical analyses will be performed using cleaned eCRF data as well as non-CRF data (ie, biopsy data from the central laboratory and pharmacokinetic (PK) data).

The primary analysis will occur after the last subject last visit (LSLV) has been achieved across all tumor types and combinations.

Additional analyses of the data may be performed for publication or regulatory reporting purposes.

Throughout this document ‘start date’ refers to date of randomization for randomized cohorts and first dose of study treatment for non-randomized cohorts.

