### **5.2.7. Definition of on-treatment period**

Safety endpoints will be summarized based on the on-treatment period unless otherwise specified.

On-treatment period is defined as the time from the first dose of study treatment through minimum (30 days + last dose of study treatment, start day of new anti-cancer drug therapy – 1 day).

Safety data collected outside the on-treatment period as described above will be listed and flagged in listings but not summarized.

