#### **5.3.2.4. Exposure**

No imputation will be done for first dose date. Date of last dose of study drug, if unknown or partially unknown, will be imputed as follows:

- If the last date of study drug is completely missing and there is no End of Treatment eCRF page and no death date, the patient should be considered to be ongoing and use the cut-off date for the analysis as the last dosing date
- If the last date of study drug is completely or partially missing and there is EITHER an End of Treatment eCRF page OR a death date available (within the cut-off date), then imputed last dose date is:
  - = 31DECYYYY, if only Year is available and Year < Year of min (EOT date, death date)
  - = Last day of the month, if both Year and Month are available and Year = Year of min (EOT date, death date) and Month < the month of min (EOT date, death date)
  - = min (EOT date, death date), for all other cases.

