### **5.3.3.4. Date of start of new anti-cancer therapy**

Incomplete dates for start date of new anti-cancer therapy (drug therapy, radiation, surgery) will be imputed as follows and will be used for determining censoring dates for efficacy analyses and in the derivation of the end of on-treatment period. PD date below refers to PD date by investigator assessment.

- The end date of new anti-cancer therapy will be included in the imputations for start date of new anti-cancer therapy. If the end date of new anti-cancer therapy is
  - completely missing then it will be ignored in the imputations below
  - partially missing with only year (YYYY) available then the imputations below will consider 31DECYYYY as the end date of the new anti-cancer therapy
  - partially missing with only month and year available then the imputations below will consider the last day of the month for MMMYYYY as the end date of the new anti-cancer therapy
- For patients who have not discontinued study treatment at the analysis cut-off date, last dose of study treatment is set to the analysis cut-off date in the imputations below.
- If the start date of new anti-cancer therapy is completely or partially missing, then the imputed start date of new anti-cancer therapy is derived as follows:
  - Start date of new anti-cancer therapy is completely missing  
Imputed start date = min [max(PD date + 1, last dose of study treatment + 1), end date of new anti-cancer therapy]
  - Only year (YYYY) for start of anti-cancer therapy is available  
IF YYYY < Year of min [max(PD date + 1, last dose of study treatment + 1), end date of new anti-cancer therapy] THEN imputed start date = 31DECYYYY;  
ELSE IF YYYY = Year of min [max(PD date + 1, last dose of study treatment + 1), end date of new anti-cancer therapy]  
THEN imputed start date = min [max(PD date + 1, last dose of study treatment + 1), end date of new anti-cancer therapy]  
ELSE IF YYYY > Year of min [max(PD date + 1, last dose of study treatment + 1), end date of new anti-cancer therapy]  
THEN imputed start date = 01JANYYYY
  - Both Year (YYYY) and Month (MMM) for start of anti-cancer therapy are available  
IF  
    YYYY = Year of min [max(PD date + 1, last dose of study treatment + 1), end date of new anti-cancer therapy], AND  
    MMM < Month of min [max(PD date + 1 day, last dose of study treatment + 1 day), end date of new anti-cancer therapy]  
THEN  
    imputed start date = DAY (Last day of MMM) MMM YYYY;  
ELSE IF  

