**Duration of exposure to PF-04518600 (weeks) =**

(last dose date of PF-04518600 – first dose date of PF-04518600 + 14)/7

**Cumulative dose** is the sum of the actual doses of PF-04518600 received overall.

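### For an analysis placed after last subject last visit, the two rules that set a missing last dose to the cut-off can only give a wrong date when they fire; few patients are likely to be affected, but the fix is nearly free

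*SAP*

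**What the plan says.** Section 2 sets the timing ("The primary analysis will occur after the last subject last visit (LSLV) has been achieved across all tumor types and combinations") and the state of the data ("Statistical analyses will be performed using cleaned eCRF data").

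Section 5.3.2.4 has a branch with three joint conditions: "If the last date of study drug is completely missing and there is no End of Treatment eCRF page and no death date". When all three hold, "the patient should be considered to be ongoing and use the cut-off date for the analysis as the last dosing date". Patients with an End of Treatment page or a death date go to a different branch, which uses those dates.

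Section 5.3.3.4, on missing or partial start dates of new anti-cancer therapy, has a related rule with a different trigger: "For patients who have not discontinued study treatment at the analysis cut-off date, last dose of study treatment is set to the analysis cut-off date". A wholly missing start date then becomes the later of the day after progression and the day after last dose, capped by the end date of the new therapy if there is one.

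The last-dose date is used in:
- duration of exposure (Sections 6.5.3.1 to 6.5.3.5), for example "last dose date of PF-04518600 – first dose date of PF-04518600 + 14" days, divided by 7;
- the window for safety summaries in Section 5.2.7: "On-treatment period is defined as the time from the first dose of study treatment through minimum (30 days + last dose of study treatment", or the day before new anti-cancer drug therapy if that is earlier;
- the 90-day window in the immune-related event definition (Appendix 1, Table 15), which applies whether or not new drug therapy has started;
- the choice of intended dose intensity for CMP-001 (Section 6.5.3.5).

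**The concern.** Treating an open record as ongoing makes sense at a data cut taken while patients are still being dosed. Once every patient has had the last visit, a record with no last-dose date, no End of Treatment page and no death date belongs to someone who was lost, withdrew or has incomplete data. Setting the last dose to the cut-off then dates it at or after the end of the whole study, however early the patient stopped.

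The rule also passes over better information. Section 3.4.1 defines last dose through non-zero doses, and Section 6.5.3 derives cycles from visit-level exposure pages.

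At stake are the exposure summaries and every summary restricted to the on-treatment period: treatment-emergent events, laboratory grades, liver tests, ECG and concomitant medications. Events long after the true last dose could be counted as treatment-emergent. Section 5.3.3.4 can also disable the safeguard that normally closes that period, because a wholly missing start of new therapy can be placed after the cut-off.

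**Working it through.** The SAP gives no figure for the effect of these rules, so there is nothing to reproduce. Its formulas are applied to assumed dates.

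**Inputs**
- Cut-off: assumed 22-Feb-2022, the date of SAP version 6. The SAP does not fix a calendar date. A later cut-off adds the same amount to every line.
- Early patient: Section 2.2.4 reports Combination A Phase 1b complete by 30 September 2016. With an 8-week DLT period, first dose was no later than about 6 Aug 2016.
- Combination F patient: assumed first dose 27-Feb-2019, the date of protocol amendment 8.
- Late entry: assumed first dose 17-Dec-2020.
- True last dose: assumed at week 6, 24, 52 or 104.

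**Duration of exposure**, every-2-week drug: (last − first + 14)/7 weeks.

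| First dose | Imputed exposure | True exposure | Excess |
|---|---|---|---|
| 6 Aug 2016 | (2026 + 14)/7 = 291.4 wk | 8, 26, 54, 106 wk | 5.4, 5.1, 4.5, 3.5 y |
| 27 Feb 2019 | (1091 + 14)/7 = 157.9 wk | 8, 26, 54 wk | 2.9, 2.5, 2.0 y |
| 17 Dec 2020 | (432 + 14)/7 = 63.7 wk | 8, 26, 54 wk | 1.1, 0.7, 0.2 y |

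The SAP's own measures then disagree for one patient. If the early patient received two cycles only, intended duration of avelumab runs to the end of cycle 2, 56/7 = 8.0 weeks, while duration of exposure is 291.4 weeks.

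**Effect on a cohort mean**, one affected patient with 12 weeks of true exposure: (291.4 − 12)/28 = 10.0 weeks in a 28-patient cohort (A1 to A3), and (157.9 − 12)/20 = 7.3 weeks in a 20-patient Combination F cohort. A median would barely move; the maximum would be an artefact.

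**On-treatment period.** With no known new drug therapy, the excess equals the shift in last dose. If new drug therapy is known to start 8 weeks after the true last dose, the period ends on day 55 after that dose instead of day 30, an excess of 56 − 1 − 30 = 25 days. The 90-day immune-related window has no such cap and moves by the full shift.

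**Dose intensity.** For the four IV drugs, cumulative dose and relative dose intensity use recorded doses and the last cycle with a non-zero dose, so nothing changes. For CMP-001 the intended intensity is 40, 30 or 20 mg per cycle, chosen by last minus first dose date. A patient given only a full cycle 1 has 40 mg over 4 weeks: 100 × 40/40 = 100%. With the last dose at the cut-off the 20 mg value applies: 100 × 40/20 = 200%.

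**Efficacy (Section 5.3.3.4).** With documented progression and a wholly missing therapy start, the imputed start is either the therapy's end date, when that falls on or before progression, or a date after progression. This is so whichever last dose is used, so outcomes do not change. Without progression, the start moves past the cut-off, and censoring is lost, only if discontinuation is unrecorded, the start date is wholly missing and no end date caps it. Scans after the switch are also needed for response or censoring dates to change. Where a year or month is recorded, the substitution cannot move the start beyond the end of that year or month.

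**The case against.** The strongest reply is that the rules will almost never fire. Section 5.3.2.4 needs three facts together, and cleaned data after LSLV should leave few or no such records. Section 3.4.1 already defines last dose as the last non-zero dose, so a patient with dated doses need not reach the branch. Section 5.3.3.4 is triggered by absence of discontinuation, not by a missing End of Treatment page, and Section 6.5.2.1 shows that discontinuation is recorded with its reason, so lost or withdrawn patients are not caught automatically. Section 2 also allows further analyses, for which an ongoing rule may be needed. All of this stands, and it limits how often the error occurs. It does not make the date right when a rule does fire, and the SAP does not say that dated administrations take precedence over the cut-off.

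A reader might infer more than the SAP supports:
- That exposure is inflated by years across the trial. The count is unknown, and patients with a death date or an End of Treatment page are outside the Section 5.3.2.4 branch.
- That one such patient more than doubles a 12-week cohort mean. In the 28-patient cohorts that fit an early entrant it goes from 12 to about 22 weeks.
- That the response-rate tests are at risk. Only the narrow case above could reach them.
- That the sentence in Section 2 is wrong. It is not; the text to change is in Sections 5.3.2.4 and 5.3.3.4.

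**Conclusion.** The point holds as a minor inconsistency. For the analysis that Section 2 plans, no patient can be ongoing, so both cut-off substitutions give a false date whenever they apply. For an affected patient the error is roughly 0.2 to 5.4 years in duration of exposure and the immune-related window. It is the same in the on-treatment period unless a known new drug therapy closes it. CMP-001 relative dose intensity can double. These sizes rest on the assumed cut-off and first-dose dates and on assumed true last doses. The number of affected patients is not given and is probably very small. Cumulative dose and relative dose intensity of the IV drugs are unaffected, and any effect on best response, PFS or duration of response is confined to the rare combination of gaps described above.

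**What to change.** For the post-LSLV analysis, replace the first bullet of Section 5.3.2.4. First query the missing End of Treatment or last-dose record. If it stays missing, use the date of the last recorded non-zero administration of that drug, flagged in listings. If none is recorded, use a date no later than last contact. In Section 5.3.3.4, use the same derived last dose in place of the cut-off. Keep the ongoing rule in both sections only for data cuts before LSLV.

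The cost is about two sentences in the SAP and a small programming change. No new data are needed.
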